9.2 Replacement of subjects

Subjects screened but not randomized will be replaced. Subjects withdrawn after receiving the third infusion will not be replaced but will be followed if they provide consent.

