3.0 STUDY PLAN

3.1 Study design

This is a single center, randomized, double blind, placebo controlled, parallel-group, out-patient study in male and female subjects aged 50 to 84 years with amnesic-mild cognitive impairment. Subjects will be randomized to receive either an infusion of IVIG at 0.4 g/kg or 0.9% saline solution (placebo) every 14 days for two months for a total of five infusions.

Fifty subjects will be enrolled and randomized in a 1:1 IVIG 2.0 g/kg: placebo ratio. Twenty-five subjects will receive IVIG and 25 subjects will receive placebo.

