5.2 Enrollment

A subject is considered enrolled when they have been randomized and received any amount of study medication (i.e., IVIG or placebo) by infusion.

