7.13 Early termination from the study

Every attempt should be made to follow each subject through the final visit 12, and subsequently visit 15 of the extension study. In the event of early withdrawal from the subject for any reason, an Early Termination Visit should be completed for criteria of withdrawal. If the subject withdraws due to an AE, every attempt should be made to follow the subject until the AE resolves or until the investigator deems that the AE is stable or determined the AE to be chronic. All SAEs will continue to be followed until the end of the study (Visit 12, 15, or ET visit) or until the SAE has resolved or the investigator deems the event to be stable or chronic.

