9.0 WITHDRAWAL AND REPLACEMENT OF SUBJECTS

9.1 Criteria for subject withdrawal

In accordance with the Declaration of Helsinki and other applicable regulations, a subject has the right to withdraw from the study at any time and for any reason. If a subject requests or decides to withdraw, every attempt will be made to complete an early termination visit.

The investigator has the right to withdraw subjects from the study if a subject:

- Is in significant violation of the protocol
- Experiences an intolerable AE or SAE
- Is non-compliant
- Withdrawal of consent
- Lost to follow up
- Death

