15.0 STATISTICAL ANALYSIS

15.1 Primary endpoint

The aim of the primary efficacy analysis is to demonstrate an advantage for subjects treated with IVIG over subjects treated with placebo at the end of the study as measured by change in ventricular volume. The primary efficacy analyses will be performed on the intent-to-treat (ITT) population. The ITT population is defined as all subjects who were randomized, received three or more infusions, and had a brain MRI at baseline and at 24 months.

Annualized percent change in total ventricular volume (APCV) is the primary biomarker of interest. Brain MRI will be obtained at baseline, 12 months, 24 months, 36 months, 48 months, and 60 months. Differences between the IVIG and placebo group at month 12, 24, 36, 48, and 60 will be analyzed using a 2 x 2 analysis of variance. Participants will also be classified as early MCI (EMCI) if baseline CDR-SB is less than 1.5, and late MCI (LMCI) if CDR-SB is greater than or equal to 1.5.

Treatment (IVIG, placebo), MCI status (EMCI, LMCI), and the treatment X MCI status interaction will be included in the model. If the interaction is statistically significant ($p < 0.05$), MCI status will be stratified and differences in APCV between the groups compared within each stratum.

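### Section 9.2 has no rule for subjects randomised and withdrawn with 0-2 infusions, and the three-infusion condition in section 15.1 takes them out of the primary comparison

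*Combined protocol and SAP*

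**What the plan says.** Section 9.2 consists of two sentences. The first is "Subjects screened but not randomized will be replaced". The second bars replacement, and offers continued follow-up, once the third infusion has been given: "Subjects withdrawn after receiving the third infusion will not be replaced but will be followed if they provide consent". Neither sentence covers a subject who is randomised and then withdraws before that infusion.

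Other sections bear on this group:

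- Section 5.2 counts those who received any drug as part of the trial: "A subject is considered enrolled when they have been randomized and received any amount of study medication".
- Section 15.1 defines the so-called ITT population as "all subjects who were randomized, received three or more infusions, and had a brain MRI at baseline and at 24 months".
- Section 7.13 sets a follow-up aim with no infusion threshold: "Every attempt should be made to follow each subject through the final visit 12, and subsequently visit 15 of the extension study".
- Section 9.1 adds, also without a threshold: "If a subject requests or decides to withdraw, every attempt will be made to complete an early termination visit".
- Section 3.1 fixes the size: "Twenty-five subjects will receive IVIG and 25 subjects will receive placebo". Section 16.0 bases its 82% power on the same 25 per arm and makes no allowance for dropout.

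**The concern.** A cut-off at the third infusion in section 9.2 has little purpose unless earlier leavers are handled differently. The same cut-off appears in the definition of the primary analysis set. Taken together, the two rules suggest that a subject who leaves after one or two infusions need not count towards the trial.

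That matters because the cut-off is reached after randomisation and under treatment. The protocol anticipates adverse events during infusion (section 6.10), expects reactions like those of other IVIG products (section 6.1), and lists an intolerable adverse event among the grounds for withdrawal (section 9.1). Leaving before the third infusion could therefore be more common with IVIG than with saline. A comparison restricted to subjects who got past that point is no longer protected by randomisation.

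Conduct and analysis are separate issues here. Widening the analysis set later cannot supply month-24 scans for subjects whom the site, relying on section 9.2, had stopped following.

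**Working it through.** **Step 1. The rules by group.**

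| Group | Replaced (9.2) | Follow-up after withdrawal | Enrolled (5.2) | Primary set (15.1) |
|---|---|---|---|---|
| Screened, not randomised | Yes | Not applicable | No | No |
| Randomised, 0 infusions | Not stated | Not in 9.2; general aim in 7.13 | No | No |
| Randomised, 1-2 infusions | Not stated | Not in 9.2; general aim in 7.13 | Yes | No |
| Randomised, 3 or more | No | Yes, with consent (9.2) | Yes | Yes, if both MRIs exist |

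The last column is the only certain loss. Subjects with 0-2 infusions are outside the primary set whether or not they are replaced or followed.

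**Step 2. Whether an early termination visit helps.** Appendix C puts the third infusion on Day 28. It places the early termination visit in the month-24 column, which includes a brain MRI. A subject who leaves after infusion 1 or 2 and has that visit soon afterwards is scanned weeks after baseline. That scan is not a month-24 MRI.

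**Step 3. Numbers randomised.** If *r* early leavers were replaced, the total randomised would be 50 + *r*. The documents give no *r*. Section 5.1 does not say how a replacement would be allocated.

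**Step 4. The plan's power figure.** Inputs from section 16.0: 25 per arm, difference 120 units, two-sided alpha 0.05, power 82%. No SD is given, so the figure cannot be checked independently; it can only be solved backwards.

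- Normal approximation: power = Φ(120 / (SD × √(2/n)) − 1.96). Setting this to 0.82 at n = 25 gives SD ≈ 147.6, that is 120/147.6 = 0.81 SD.
- The t-test version gives SD ≈ 144.6, that is 0.83 SD.

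At these back-solved SDs, if early leavers are not replaced and have no month-24 scan:

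| Analysed per arm | Power, normal | Power, t test |
|---|---|---|
| 25 | 82.0% | 82.0% |
| 24 | 80.4% | 80.4% |
| 23 | 78.8% | 78.6% |
| 22 | 77.0% | 76.7% |
| 20 | 73.0% | 72.5% |

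**Step 5. Possible bias (assumed inputs, illustration only).** Suppose *k* subjects leave early in one arm only, are excluded and replaced by typical stayers, and would have differed from stayers by *D* SD.

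- Shift in arm mean = *D* × *k*/(25 + *k*).
- Standard error of the difference, in SD units = √(2/25) = 0.283.
- Type I error = P(Z > 1.96 − shift/0.283) + P(Z < −1.96 − shift/0.283).

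| *k* | *D* | Shift (SD) | Share of 0.83 SD | Two-sided type I error |
|---|---|---|---|---|
| 2 | 0.5 | 2/27 × 0.5 = 0.04 | 4% | 5.2% |
| 3 | 1 | 3/28 = 0.11 | 13% | 6.7% |
| 5 | 1 | 5/30 = 0.17 | 20% | 9.1% |

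Without replacement the shift is *D* × *k*/25, for example 3/25 = 0.12 SD for *k* = 3 and *D* = 1. That is about the same as 0.11, so the shift comes from the exclusion in section 15.1 and not from adding subjects. If *D* = 0, or if the same kind of leaving occurs equally in both arms, the bias is zero.

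**The case against.** The strongest reply is that section 9.2 never says early leavers are replaced or lost to follow-up. Its first sentence names only non-randomised subjects as replaceable, which could equally mean that nobody else is. Section 7.13 asks for each subject to be followed through visit 12. Adding subjects does no harm if every randomised subject is kept and analysed. All of this stands, and it limits what can be claimed.

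A reader might infer four stronger things that the documents do not support:

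- *That early leavers are replaced and dropped from follow-up as a rule.* Section 9.2 is silent, and section 7.13 points the other way on follow-up.
- *That section 9.2 by itself breaks the randomised comparison.* The certain exclusion comes from section 15.1.
- *That more than 50 subjects were randomised.* This requires both an early leaver and a replacement, and neither is documented.
- *That tolerability is overstated.* Section 10.1 records adverse events from randomisation onward, and the three-infusion condition is attached to the primary efficacy analysis only.

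The general aim in section 7.13 does not settle the matter. For a subject who withdraws, sections 7.13 and 9.1 specify an early termination visit. The only explicit undertaking to keep following a withdrawn subject for trial purposes is the one in section 9.2, and it is limited to those past the third infusion.

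It is also fair to say that the remedy may come late. Amendment 8 already refers to conversions at years 1 and 2, and Amendment 9 carries a 2016 committee approval.

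**Conclusion.** The point holds as a gap in section 9.2 combined with a stated exclusion in section 15.1. The protocol does not say what happens to randomised subjects who leave with 0-2 infusions, it permits a reading under which they are replaced and not followed, and it removes them from the primary analysis. That analysis is therefore not intention-to-treat.

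The exclusion can bias the result, but the amount is unknown: the documents give no withdrawal rate, no split by arm, and no link between early leaving and ventricular change. The illustrated range, 5.2% to 9.1% type I error, rests on 2-5 leavers confined to one arm with outcomes 0.5-1 SD different. The comparison with 0.83 SD also assumes that the standardised effect behind section 16.0, which is stated for ventricular volume, carries over to the annualised percent change now used as the endpoint. These figures show scale and are not a forecast.

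**What to change.** In section 9.2, state that only subjects not yet randomised are replaced. If the sponsor prefers to top up, state that any added subject is additional and that the subject who left is retained. State also that every consenting randomised subject is followed on the month-12 and month-24 MRI visits whatever number of infusions was received, and bring sections 9.2 and 7.13 into line.

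In section 15.1, remove the three-infusion condition, define the ITT population as all randomised subjects in their assigned arm, and name a missing-data method for those without a month-24 scan. The three-infusion set can remain as a labelled supportive analysis.

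If enrolment is closed, report by arm the numbers randomised, leaving before the third infusion, and replaced, and include all randomised subjects in the primary analysis with the stated missing-data method.

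The cost is a short amendment and a few visits already in the schedule. There will be slightly fewer fully treated subjects. Power falls somewhat below 82% if early leavers have no month-24 scan, for example to about 77% at 22 per arm.

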10.0 ADVERSE EVENTS

10.1 Adverse event definition

An AE is any untoward event that occurs any time after randomization to the double blind treatment until the end of study (visit 12, visit 15, or ET visit). The event need not have a causal relationship with the study drug or treatment. Adverse events include, but are not limited to clinically significant changes in clinical status, physical or neurological examinations, ECG, abnormal laboratory findings, exacerbations of underlying disease, and drug interactions,

dependency, misuse and abuse. All AEs must be documented on the Adverse Event page of the CRF and in the subject's medical notes. Each AE is evaluated for duration, severity, seriousness, relatedness to study drug, and action taken. The investigator may be asked to provide follow-up information.

10.2 Serious adverse event (SAE) definition

A serious adverse event is one that at any dose (including overdose):

- Results in death
- Is life-threatening¹
- Requires inpatient hospitalization or prolongation of existing hospitalization
- Results in persistent or significant disability or incapacity²
- Is a congenital anomaly/birth defect
- Is a medically important condition:
 - Suspected transmission of an infectious agent,
 - Thromboembolic events,
 - Cerebral hemorrhage resulting in clinical disability, or
 - Other reactions that should be reported in an expedited manner although they did not immediately result in one of the above seriousness criteria

10.3 Other relevant drug safety information:

Any safety information relating to

- Pregnancies/breastfeeding,
- Drug abuse (persistent, sporadic or intentional excessive use of a medicinal product inconsistent with the SPC or acceptable medical practice),
- Overdose (treatment exceeding the medically recommended dose),
- Medication errors (prescribing or dispensing error),
- Interactions with other medicinal products or devices
- Associated with NewGam 10%, even if no adverse drug reaction occurred.

¹"Life-threatening" means that the subject was at immediate risk of death at the time of the serious adverse event; it does not refer to a serious adverse event that hypothetically might have caused death if it were more severe.

²"Persistent or significant disability or incapacity" means that there is a substantial disruption of a person's ability to carry out normal life functions.

10.4 Adverse events severity

Severity of AEs will be assessed using the National Cancer Institute (NCI) Common Terminology Criteria for Adverse Events (CTCAE) Version 3.0 for toxicity and adverse event reporting. A copy of the CTCAE Version 3.0 can be downloaded from the CTEP homepage (<http://ctep.info.nih.gov>). AEs not corresponding to the CTCAE term will be assessed according to their impact on the subject's ability to perform daily activities as follows:

- Mild (grade 1) – the AE does not interfere in a significant manner with the subject's normal functioning level. It may be an annoyance.
- Moderate (grade 2) – the AE produces some impairment of functioning, but is not hazardous to health. It is uncomfortable or an embarrassment.
- Severe (grade 3) – the AE produces significant impairment of functioning or incapacitation and is a definite hazard to the subject's health.
- Life Threatening (grade 4) – Life threatening or disabling.
- Fatal (grade 5) Causes death of the participant.

The investigator must appraise all abnormal laboratory results for their clinical significance. If any abnormal laboratory result is considered clinically significant, the investigator must provide details about the action taken with respect to the test drug and about the patient's outcome.

10.5 Adverse event reporting

All AEs, whether observed by the investigator or reported by the patient, must be recorded, with details about the duration and intensity of each episode, the action taken with respect to the test drug, and the patient's outcome. The investigator must evaluate each adverse experience for its relationship to the test drug and for its seriousness. The initial report must be as complete as possible, including details of the current illness and (serious) adverse event, and an assessment of the causal relationship between the event and the investigational product(s). Information not available at the time of the initial report (e.g., an end date for the adverse event or laboratory values received after the report) must be documented on a follow-up form. A final report to document resolution of the adverse event is required.

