4.1 Inclusion criteria

1. Signed and dated written informed consent obtained from the subject in accordance with the local regulations. The subject's collaborative informant must also consent to participate in the study.
2. Age from 50 to <85 years.

3. Diagnosis of Mild Cognitive Impairment, Amnesic type (single or multi domain) according to Petersen criteria (Appendix B), NIA diagnostic guidelines, [15] and supported by a CDR score of 0.5.
4. Mini-Mental State Examination (MMSE) score of 24-30, inclusive.
5. Rosen Modified Hachinski Ischemic score ≤ 4 .
6. Willing to consent to ApoE testing and agree to disclose ApoE4 status. Previous ApoE testing will be accepted.
7. Receiving stable doses of medication(s) for the treatment of non-excluded medical condition(s) for at least 30 days prior to screening.
8. Agree to refrain from taking any medication, vitamin, or herbal supplement indicated for a-MCI or AD or considered to enhance cognition unless approved by the investigator for the duration of the study.
9. Ability to attend all clinical visits and have an informant capable of accompanying the subject on specific clinic visits for two years or the duration of the study.
10. The subject's collaborative informant (support person) must be someone who has known the subject for at least 4 years; agrees to have at least 2 separate communications with the study participant per month for the duration of the study (one of these communications must be in person); and attends and completes the CDR interview at 8 study visits along with the subject.
11. Fluency in English and evidence of adequate premorbid intellectual functioning.
12. Adequate manual dexterity, visual, and auditory abilities to perform all aspects of the cognitive and functional assessments.
13. Venous access suitable for repeated infusion and phlebotomy.
14. In the opinion of the investigator, the subject and informant will be compliant and have a high probability of completing the study, including all scheduled evaluations and required tests.

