7.0 EVALUATIONS BY VISIT

The overall summary of study activities by visit is provided in Appendix C at the end of the document.

Screening procedures at visit 1 will take place up to 28 days prior to Visit 2 (Day 1) dosing. Screening labs and assessments will be performed during the screening period. A brain MRI will be obtained as standard of care within 6 months prior to the screening period. The first dose of study drug is administered on Day 1. Visits 2 through 6 have a ± 1 day window and occur every 14 days over two months. The investigator will determine if a subject is suitable to continue following the missed infusion. Visits 7 through 12 (Month 4 through Month 24) have a ± 7 day window. Visits 13 through 15 (Month 36 through Month 60) have a ± 14 day window).

All study screening data from Visit 1 including laboratory results must be reviewed for study eligibility prior to receiving first dose of study drug. Visit 2 physical exams and neurological exams prior to infusion may occur within 72 hours prior to the first infusion. Prior to infusion, a review of concomitant medications and AEs takes place to ensure that no excluded medications have been added or medication discontinued or dose changed that were required to have been stable. If the subject continues to be eligible for enrollment, the subject will be randomized, infused with study medication and will remain in the infusion clinic for at least 4 hours following the start of the infusion for safety assessments on Visit 2 (Day 1).

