7.2 VISIT 2: Day 1 – First Infusion

The investigator will confirm that subjects are still eligible by reviewing all screening data. Subjects who no longer meet criteria will not be eligible for enrollment in the study.

7.2.1 Pre-dose:

- Confirm that subjects continue to meet inclusion/exclusion criteria
- Assess and record AEs
- Record concomitant medications
- Record vital signs
- Perform physical and neurological examinations (may occur within 72 hours prior to first infusion)
- Complete randomization
- The unblinded pharmacist will prepare the study drug according to the preparation instructions in Section 5.7 and will deliver the study drug to the blinded infusion administration site.

7.2.2 Study drug infusion:

- Subjects will be given the option of prophylaxis oral acetaminophen, diphenhydramine, or both 15-30 minutes prior to infusion
- Measure blood pressure, pulse rate, temperature and respiratory rate within 15 minutes prior to start of the infusion
- Administer study drug to the subject by intravenous infusion

7.2.3 Following initiation of infusion:

- Measure blood pressure and pulse rate at 15, 30, 60 and every 30 minute mark for the duration of the infusion
- Measure blood pressure, pulse rate, temperature and respiratory rate immediately post dose and prior to leaving the clinic
- Assess infusion site post infusion
- Assess and record AEs
- Subjects will remain in the clinic for at least one hour following the completion of the infusion. The subjects may leave the clinic after the observation period if the subject is medically stable.

7.3 VISIT 3 (Day 14 -Second Infusion) through VISIT 6 (Day 56 – Fifth Infusion)

- Assess and record AEs
- Record concomitant medications
- Record vital signs
- If there is any abnormality of vital signs or clinical concerns during infusion visit, the principle-investigator or sub-investigator will be paged in order to perform a clinical assessment.
- The unblinded pharmacist will prepare the study drug according to the preparation instructions and will deliver the study drug to the blinded infusion administration

7.3.1 Study drug infusion:

- Subjects will be given the option of prophylaxis oral acetaminophen, diphenhydramine, or both 15-30 minutes prior to infusion
- Measure blood pressure, pulse rate, temperature and respiratory rate within 15 minutes prior to start of the infusion
- Administer study drug to the subject by intravenous infusion

7.3.2 Following initiation of infusion:

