7.4 VISIT 7: Month 4 (±7 days)

- Assess and record AEs
- Record concomitant medications
- Record vital signs
- Perform physical and neurological examinations
- Record vital signs
- Assess and record AEs
- Record concomitant medications
- Obtain standard 12-lead ECG
- Administer MMSE, ADAS-Cog, and CDR-SB
- Obtain blood sample for routine hematology and chemistry laboratory tests
- Obtain blood sample for HIV-I & II, HCV, HBV, B19, HAV

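### After the fifth infusion no AE contact is scheduled for about 67 days, against 13 to 14 days after each earlier infusion, and Section 10.5 does not name the mandatory informant as an AE source

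*Combined protocol and SAP*

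**What the plan says.** **Sources.** Section 10.5 (Adverse event reporting) requires that "All AEs, whether observed by the investigator or reported by the patient, must be recorded". Section 10.1 is broader: "An AE is any untoward event that occurs any time after randomization to the double blind treatment until the end of study". It says nothing about who must report the event. The visit lists in Section 7 call for AEs to be assessed and recorded, again without naming a source.

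**Timing.** Section 7.0 states that "Visits 2 through 6 have a ± 1 day window and occur every 14 days over two months". The infusions after the first run from "VISIT 3 (Day 14 -Second Infusion) through VISIT 6 (Day 56 – Fifth Infusion", and each of these visits includes an AE assessment. After infusions 2 to 5 the subject may leave, if stable, once a minimum of 15 minutes of observation has passed. The next entry in Section 7 and in Appendix C is "VISIT 7: Month 4 (±7 days". No call, diary or visit is listed between the two.

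**Informant.** Under inclusion criterion 10 (Section 4.1) the informant must communicate with the subject at least twice a month, once in person, and "attends and completes the CDR interview at 8 study visits along with the subject". No part of the documents gives the informant a role in AE reporting.

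**Use of the data.** Section 15.2.2 plans a safety analysis once 25 subjects have been followed for three months, based on documented AEs.

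**The concern.** Every subject has amnestic MCI. An AE that has resolved by the next visit, with no trace on examination, ECG or laboratory test, reaches the record only if someone remembers it or reports it unprompted. For the first four infusions the subject is asked about two weeks later. For the fifth, the subject is asked after about nine and a half weeks. The person best placed to help, the informant, is already in the trial but is not named as a source.

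At stake is the completeness of AE data after the last infusion, which is one in five of all exposures. The three-month safety review is also affected, because it falls inside this interval.

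**Working it through.** **Inputs from the documents.** Infusion visits on Days 1, 14, 28, 42 and 56, ±1 day (Section 7.0, Appendix C). Visit 7 at Month 4, ±7 days (Section 7.4). Month visits counted from the first infusion (Section 3.3). 25 subjects per arm and five infusions each (Section 3.1).

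**Assumption.** The documents do not define a month. The main figure uses 30.4375 days, with the first infusion on Day 1.

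1. *The plan's own interval.* 14 − 1 = 13; 28 − 14 = 14; 42 − 28 = 14; 56 − 42 = 14 days. This agrees with the stated 14-day spacing within its window.

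2. *Interval after infusion 5.* Month 4 = 1 + 4 × 30.4375 = Day 122.75. Gap = 122.75 − 56 = 66.75 days.

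3. *Visit windows.* Visit 6 may move by 1 day and Visit 7 by 7, so 66.75 ± 8 gives 58.75 to 74.75 days.

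4. *Sensitivity to the month, without windows.*
 - First infusion counted as Day 0: 121.75 − 56 = 65.75 days.
 - 30-day months: 121 − 56 = 65 days.
 - 28-day months: 113 − 56 = 57 days.
 - Calendar months: 65 to 68 days, depending on the start date.

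5. *Ratio.* 66.75 / 14 ≈ 4.8.

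6. *Exposures affected.* 50 subjects × 5 = 250 planned infusions, of which 50 are fifth infusions: 50 / 250 = 20%.

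7. *Interim safety analysis.* Section 15.2.2 does not give the origin of its three months. Counted from the first infusion, three months is 1 + 3 × 30.4375 ≈ Day 92.3. That is 92.3 − 56 ≈ 36 days after infusion 5 and 122.75 − 92.3 ≈ 30 days before Visit 7. A subject at exactly that point has had no scheduled AE check since Day 56. Subjects already past Month 4 at the data cut have had one. Counted from the fifth infusion instead, three months would be 56 + 91.3 ≈ Day 147, after Visit 7, and this part of the point would fall away.

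8. *Informant contact in the gap.* 66.75 / 30.4375 ≈ 2.2 months at two or more communications a month gives about four contacts that could be drawn on.

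9. *Direction of any effect.* Suppose a fraction s of the AEs in the gap is captured, the same in both arms, and the true rates are a (IVIG) and b (placebo). Observed rates are s·a and s·b. Their difference is s(a − b), smaller than a − b in size when s < 1 and the rates differ. Their ratio is still a/b. The documents give no value for s, a or b, so no size follows.

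10. *Effect of one added contact at Day 70.* 70 − 56 = 14 days, then 122.75 − 70 = 52.75 days to Visit 7.

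**The case against.** A reader might infer three stronger things. None is supported.

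- *That Section 10.5 restricts AEs to investigator and patient.* It does not. The sentence imposes a duty to record and names two routes without barring others, and Section 10.1 covers any untoward event. Nor can one say that informants are never asked, since interview practice and CRF content are not in the documents.
- *That harms of the last infusion are under-counted.* No AE rate, onset time or recall rate is given. Only a risk can be stated.
- *That the treatment is made to look safer.* With the coordinator, investigator and infusion nurse blinded (Section 6.5), loss should be similar in both arms. The absolute difference may shrink, but a ratio would be roughly unchanged. The same dose is also followed by a two-week check four times per subject.

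Other points on that side have force. Visit 6 has vital signs, an infusion-site check and an AE assessment. Visit 7 has AE and medication review, examinations, ECG, hematology, chemistry and viral serology. CDR-SB is also scheduled at Visit 7, so the informant may be there. Events that meet the seriousness criteria in Section 10.2 are unlikely to be forgotten in nine weeks. Entry requires MMSE 24 to 30 and CDR 0.5, so impairment is mild. Later AE checks are four months apart, and 12 months apart after Month 24, which is longer still.

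These arguments narrow the concern to mild or transient events with onset after the subject leaves Visit 6. They do not remove it. Examinations and tests at Visit 7 do not recover a symptom that has resolved. The later, longer gaps do not directly follow an infusion, whereas this one does. No stated reason explains why the fifth infusion lacks the two-week check that the first four receive.

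**Conclusion.** The point holds as a gap in AE ascertainment of known length and unknown effect. The scheduled interval is about 67 days after infusion 5, against 13 to 14 days after the others. It applies to 20% of planned infusions, in a memory-impaired population whose mandatory informant is not named as a source. The length depends on the month convention (57 to 68 days before windows), but the contrast does not. The effect on AE counts cannot be estimated from the documents. The expectation of similar loss in both arms rests on the blind being kept, and the remark on the interim analysis rests on counting its three months from the first infusion. There is no contradiction in the plan and no effect on the primary endpoint. This is a cheap improvement to safety data collection.

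**What to change.** 1. In Appendix C, add one telephone contact with subject and informant about 14 days after Visit 6, to collect AEs and concomitant medications. Existing blinded staff should make it. The fifth infusion then gets the same AE check as the first four, and the result is available to the three-month safety review. About 53 days remain before Visit 7.
2. In Section 10.5, add the informant as an AE source at each visit where the informant attends for the CDR. Tie the wording to attendance, not to a list of visit numbers. Criterion 10 commits the informant to eight visits, while Appendix C shows CDR-SB at Visits 1 and 7 to 15 (1 + 9 = 10). Subjects who convert to AD have no CDR at Visit 8 and do not attend Visits 10 and 11 (Section 8.0).
3. If infusions are already complete, as the amendment history suggests (Amendment 8 refers to conversions at year 2), apply the informant wording to the remaining visits and disclose the longer interval after infusion 5 in the safety report.

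Cost: about 50 short calls and one added sentence. The downside is slightly more coordinator work and a few more non-serious AEs to record in both arms. Dosing, infusion visits and patient care do not change.
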